Pregnancy testing	X	X*			X	Section 8.4.4.2; at the indicated visits, only female participants who have reached menarche will undergo a urine pregnancy test. A positive urine test must be confirmed by a serum test. *Day 1 testing will be performed only if the interval between this visit and screening is > 2 weeks.	

Table 3: Schedule of Activities: Vehicle-Controlled Period (Continued)

Visit Day (Range)	Screening	VC Period				Notes and Protocol Section
	Days -28 (+ 7 ^a) to -1	Day 1/ Baseline	Wk 2 (± 3 d)	Wk 4 (± 3 d)	Wk 8 ^b /ET (± 3 d)	

Note: Unscheduled visits may occur at any time at the investigator's discretion, and appropriate clinical and laboratory tests may be performed as clinically indicated.

^a For prior medications that require a 4-week washout period (see Section 5.2, Exclusion Criterion 6b), a 35-day screening period is allowed.

^b Week 8 is the baseline for participants eligible to continue in the LTS period (IGA score = 0-4 and BSA = 0%-20%).

Table 4: Schedule of Activities: Long-Term Safety Period

Visit Day (Range)	LTS Period					Unscheduled Visit	Safety Follow-Up 30 (+ 7) Days After Last Study Cream Application ^a	Notes and Protocol Section
	Wk 12 (± 7 d)	Wk 16, 20, and 24 (± 7 d)	Wk 28, 32, and 36 (± 7 d)	Wk 40, 44, and 48 (± 7 d)	Wk 52/ EOT/ET (± 7 d)			
Administrative procedures								
Contact IRT	X	X	X	X	X	X	X	Section 8.1.3.
Prior/concomitant medications and procedures	X	X	X	X	X	X	X	Section 6.6.
Apply study cream at site	X	X	X	X				Section 6.1; only for participants with active AD lesions at time of visit; apply the first (morning) application under direct site staff supervision.
Weigh and dispense study cream; dispense diary cards	X	X	X	X				Section 6.1 and Section 8.1.4.
Collect and weigh study cream; collect diary cards	X	X	X	X	X			Section 6.1.
Record start and end dates of treatment cycle(s)	X	X	X	X	X			Section 6.1; the start/end date will have been recorded by the participant. The end date should be 3 days after lesions clear; however, if this 3-day window is during a study visit and IGA score = 0, stop treatment and record the date of the study visit as the treatment cycle end date.
Assess compliance	X	X	X	X	X			Section 6.4.
Safety assessments								
AE assessments	X	X	X	X	X	X	X	Section 8.4.1.
Comprehensive physical examination					X			Section 8.4.2.1.

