^a Except for participants who have been in an observation/no treatment cycle with a total IGA score of 0 (clear) from Week 48 or earlier until Week 52; such participants should complete the safety follow-up and Week 52/EOT visits together. In practice, this would mean conducting all Week 52/EOT visit assessments plus the pregnancy test at the Week 52/EOT visit.

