Following the end of treatment (Week 52/EOT or ET), all participants will have a safety follow-up visit 30 days later to evaluate safety and duration of response. One exception to this would be for participants who have been in an observation/no treatment cycle with an IGA score of 0 (clear) from Week 48 or earlier until Week 52; such participants could complete the safety follow-up and Week 52/EOT visits together. In practice, this would mean conducting all Week 52/EOT visit assessments plus the pregnancy test at the Week 52/EOT visit.

[Figure 1](#) presents the study design schema, and [Table 3](#) (VC period) and [Table 4](#) (LTS period) present the SoA.

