The start and end dates of treatment applications will be captured by the participant. Once the lesions clear, participants should continue to apply study cream for an additional 3 days to the areas of the body where lesions were last present before discontinuing treatment. If this 3-day window is during a study visit and the IGA score is 0, as assessed by the investigator, treatment is to be stopped. The date of the study visit will be recorded as the treatment cycle end date. If a lesion recurs, then treatment should be resumed at the first sign of recurrence.

At any time during the LTS period, if a participant's new areas to be treated in addition to the areas identified at the previous visit exceed 20% BSA, then the participant should be discontinued from study treatment and complete the EOT assessments.

No study treatment adjustments are allowed except for temporary drug discontinuation, if needed (eg, for management of an AE; see Section 6.5).

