8.4.1. Adverse Events

Adverse events will be monitored from the time the participant signs the ICF (or assent) until at least 30 days after the last application of study cream. Adverse events that begin or worsen after informed consent should be recorded on the Adverse Events Form in the eCRF regardless of the assumption of a causal relationship with the study cream. Conditions that were already present at the time of informed consent should be recorded on the Medical History Form in the eCRF. Adverse events (including laboratory abnormalities that constitute AEs) should be described using a diagnosis whenever possible rather than by individual underlying signs and symptoms.

Adverse events will be reported by the participant (or, when appropriate, by a caregiver, surrogate, or the participant's legally authorized representative). The investigator and any qualified designees are responsible for detecting, documenting, and recording events that meet the definition of an AE or SAE and remain responsible for following up on AEs that are serious, considered related to the study cream/procedures, or that caused the participant to discontinue the study cream. Care will be taken not to introduce bias when detecting AEs and/or SAEs.

Open-ended and nonleading verbal questioning of the participant, such as "How are you feeling?", is the preferred method to inquire about AE occurrences. Adverse events may also be detected when they are volunteered by the participant during the screening process or between visits or through physical examinations, laboratory tests, or other assessments. The definition, reporting, and recording requirements for AEs are described in Section 9.

All SAEs will be reported to the sponsor or designee within 24 hours. The investigator will submit any updated SAE data to the sponsor within 24 hours of it being available.

After the initial AE/SAE report, the investigator is required to proactively follow each participant at subsequent visits/contacts. All SAEs will be followed until resolution, stabilization, the event is otherwise explained, or the participant is lost to follow-up (as defined in Section 7.3).

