8.9. Follow-Up

8.9.1. Safety Follow-Up

The safety follow-up period is the interval between the Week 52/EOT or ET visit and the scheduled follow-up visit, which should occur 30 days after the Week 52/EOT or ET visit, with the following 2 exceptions:

- Follow-up visit should occur at the Week 52/EOT visit for participants who have been in an observation/no treatment cycle with an IGA score of 0 (clear) from Week 48 or earlier until Week 52
- Follow-up visit should occur 30 days after the last application of study cream if the Week 52/EOT or ET visit was not performed.

Adverse events and SAEs must be reported up until 30 days after the last application of study cream; ongoing AEs and SAEs must be followed up until toxicities resolve, return to baseline, or are deemed irreversible, whichever is longer. Reasonable efforts should be made to have the participant return for the follow-up visit and report any AEs that may occur during this period.

9. ADVERSE EVENTS: DEFINITIONS AND PROCEDURES FOR RECORDING, EVALUATING, FOLLOW-UP, AND REPORTING

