9.2. Adverse Events

9.2.1. Adverse Event Definitions

A TEAE is any AE either reported for the first time or worsening of a pre-existing event after first application of study drug and within 30 days after the last dose of study drug. For participants who cross over treatments, the first application date is period specific, and the end date is 30 days after the last application date in this period or the first application date in the next period, whichever comes first. Analysis of AEs (as discussed below) will be limited to TEAEs, but data listings will include all AEs regardless of their timing in relation to study drug administration.

Adverse events will be tabulated by MedDRA PT and SOC. Severity of AEs will be graded using the NCI CTCAE v5. The CTCAE (Grade 1 to 5) is used for this study. The CTCAE reporting guidelines and grading details are available on the Cancer Therapy Evaluation Program website.

The subset of AEs considered by the investigator to be related to study drug will be considered treatment-related AEs. If the investigator does not specify the relationship of the AE to study drug, the AE will be considered treatment-related. The incidence of AEs and treatment-related AEs will be tabulated. In addition, serious AEs will also be tabulated.

Any missing onset date, causality, or severity must be queried for resolution. Unresolved missing causality and severity will be handled according to the following rules:

- An unresolved missing causality will be considered treatment-related.
- An unresolved missing severity will be identified as an unknown severity.

For purposes of analysis, all AEs will be considered TEAEs unless the AE can unequivocally be defined as not treatment-emergent.

Application site reactions are AEs that occur at the site of drug application. A summary of ASRs will be provided. Exposure-adjusted summaries will also be provided for the safety population, including cumulative TEAEs and cumulative ASRs.

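### The exception merging the safety follow-up with Week 52 is tied to a visit label, not to days since last application, so the merged visit can fall before day 30

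*Protocol*

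**What the plan says.** Table 4 of the Protocol times the last visit as "Safety Follow-Up 30 (+ 7) Days After Last Study Cream Application". The window has a plus side and no minus side. Section 8.4.1 has adverse events monitored "until at least 30 days after the last application of study cream", Section 8.9.1 states that "Adverse events and SAEs must be reported up until 30 days after the last application of study cream", and Section 9.4 sets the same limit for serious events. The SAP (Section 9.2.1) counts events as treatment-emergent when they occur "within 30 days after the last dose of study drug".

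One group is excepted from the separate visit: children in an observation cycle "with a total IGA score of 0 (clear) from Week 48 or earlier until Week 52". The exception appears three times. Footnote a of Table 4 says "such participants should complete the safety follow-up and Week 52/EOT visits together". Section 8.9.1 likewise says that the follow-up *should* take place at Week 52. Section 4.1 is permissive: "such participants could complete the safety follow-up and Week 52/EOT visits together".

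A treatment cycle can end at the Week 48 visit itself. Under Section 6.1, if the three days of application after clearing overlap a visit and the IGA is 0, treatment stops, and "The date of the study visit will be recorded as the treatment cycle end date".

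**The concern.** The exception assumes that a child clear and untreated from Week 48 is about a month past the last application by Week 52. It tests this by visit name and not by counting days. Week 48 and Week 52 are four weeks apart, each has its own window, and a child may have used cream until just before Week 48. The merged visit can then come before the 30 days that every other safety rule in the two documents uses.

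What is at stake is the completeness of adverse event data at the end of a long-term safety period in children. Events between an early merged visit and day 30 fall inside the SAP's treatment-emergent window, but no scheduled visit or call is left to elicit them.

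**Working it through.** **Inputs**
- Nominal interval from Week 48 to Week 52: (52 − 48) × 7 = 28 days.
- Visit windows: ±7 days at Week 48 and ±7 days at Week 52 (Table 4); ±10 days at Week 52 under COVID-19 rules (Appendix C).
- Required minimum: 30 days from last application (Table 4, Sections 8.4.1, 8.9.1 and 9.4).
- Latest possible last application: the evening before the Week 48 visit. An IGA of 0 at the visit puts the child into observation (Section 4.1), on-site application is only for children with active lesions (Table 4), and the morning application is not made at home on a visit day (Section 6.1.1).

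**Formula.** Let d be the days from last application to the actual Week 48 visit, so d is at least 1 for this group. Let e48 and e52 be the deviations of the two visits from their target dates. Then

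gap = 28 + d + e52 − e48.

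**The plan's own figure.** The Amendment 3 rationale (Appendix F, used here only for intent) gives an aim of at least 30 days and expects Week 52 to fall at approximately 30 days or more after the last application. With d = 1 and both visits on target, the gap is 28 + 1 = 29 days. That fits the approximate wording but not the minimum, before any visit window is used.

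**Results for d = 1**

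| Case | Gap (days) | Short of 30 by |
|---|---|---|
| Both visits on target | 28 + 1 = 29 | 1 |
| Week 48 on target, Week 52 seven days early | 28 + 1 − 7 = 22 | 8 |
| Week 48 seven days late, Week 52 seven days early | 28 + 1 − 7 − 7 = 15 | 15 |
| Week 48 seven days late, Week 52 ten days early (COVID-19) | 28 + 1 − 10 − 7 = 12 | 18 |
| Week 48 seven days early, Week 52 seven days late | 28 + 1 + 7 + 7 = 43 | none |

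**Who is affected.** On schedule, 28 + d reaches 30 once d is 2. At the standard extremes the gap is 14 + d, so 30 days is assured once d is 16. With the COVID-19 window it is 11 + d, so d must be 19. A child untreated since Week 44 (last application the evening before that visit) has a minimum gap of 56 + 1 − 14 = 43 days, or 56 + 1 − 17 = 40 under the COVID-19 window, and always passes.

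**What covers the remaining days.** The reporting duty in Sections 8.4.1, 8.9.1 and 9.4 runs to day 30 for everyone. But Table 4 schedules nothing after the merged visit, and Section 4.2 treats a child who has completed the safety follow-up visit as having completed the study. Section 9.4 releases investigators from actively seeking events after study participation ends, which it explains as after the safety follow-up visit *or* 30 days after last application. For these children the merged visit is the safety follow-up visit, so on one reading the release begins there.

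**The case against.** The strongest reply is that this is a deliberate, stated exception. Footnote a is attached to the very column that sets the 30-day timing, and Sections 4.1 and 8.9.1 repeat it. For visit timing, a general rule with an express exception is not a contradiction. The merged visit keeps its full content: adverse events, vital signs, chemistry and hematology, with the pregnancy test added. On schedule the shortfall is one day, and the 15-day gap needs late use of cream and both visits at opposite ends of their windows. All of that stands. It does not reach the adverse event rules, which carry no exception and still run to day 30.

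Four stronger readings are tempting, but the documents do not support them:
- *The gap is 28 days on schedule and 14 at the extremes.* This counts from the recorded cycle end date. The 30-day rules count from the last application, which for these children is at the latest the evening before.
- *The merged visit is the last contact and ends safety collection.* No text says so. Section 8.9.1 restates the 30-day reporting duty directly after the exception, and Section 8.7 allows unscheduled visits. It is the last scheduled contact.
- *Treatment-emergent events will be undercounted.* This is possible but not shown. The SAP's 30 days decide which events count and set no visit. Spontaneous reports would still be included.
- *Pregnancies will be missed.* Testing applies only to girls past menarche in a trial of children under 12 at screening, and the test is done at the merged visit. This is a minor matter.

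**Conclusion.** The point holds as a gap in wording. The exception cannot guarantee the 30-day minimum, because it is conditioned on the Week 48 label and not on days since last application. For a child who last applied cream on the evening before Week 48, the merged visit comes at day 29 on schedule, at day 15 at the standard window extremes, and at day 12 under the COVID-19 window. On schedule only such a child is affected. With the standard windows a child can be affected if the last application was within 15 days before Week 48.

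The consequence is limited. The reporting duty continues, but active enquiry may not, so events in the uncovered days may depend on families volunteering them. The documents do not say how many children stop close to Week 48 or how visit dates spread within their windows, so neither the number affected nor the number of events can be calculated. Any undercount is probably small. The figures assume that visits stay within their windows and that the rules on visit-day application are followed.

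**What to change.** Footnote a of Table 4, Section 4.1 and Section 8.9.1 must be reconciled with the 30-day rule in Table 4, Section 8.4.1 and Section 9.4. Either of two wordings would close the gap: a merged visit counts as the safety follow-up only where the stated 30-day window since last application has closed, or the text says that active safety collection continues to day 30 for children whose merged visit comes earlier. The same edit should settle *should* against *could*, and should make clear which of the two end points in Section 9.4 applies to these children. Which arrangement suits the trial is for the sponsor to decide.

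The cost is Protocol wording and a matching site instruction. The SAP definition needs no change.

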2. INTRODUCTION

2.1. Background

Ruxolitinib cream is a topical formulation of ruxolitinib phosphate under development for the treatment of patients with AD and vitiligo and was investigated earlier in alopecia areata and plaque psoriasis. Ruxolitinib phosphate is an inhibitor of the JAK family of protein tyrosine kinases. Inflammatory cytokines are strongly implicated in the pathogenesis of several dermatologic diseases. Because JAKs serve to translate extracellular signals from a number of relevant cytokines and growth factors upregulated in inflammatory diseases such as AD, alopecia areata, plaque psoriasis, and vitiligo, JAK inhibitors represent potential therapeutic agents for these disease states (Howell et al 2019).

Atopic dermatitis is a chronic, recurring, inflammatory, and highly pruritic skin condition that affects up to 25% of children and up to 12% of adults worldwide (Eichenfield et al 2014, Hanifin et al 2007, Harrop et al 2007, Rönmark et al 2012, Vinding et al 2014) and is one of the most common dermatoses encountered by pediatric health care providers. Although not life-threatening, patients with AD are at a higher risk for the development of other potentially life-threatening disorders such as asthma and/or food allergy (Spergel 2010). According to the recent Global Burden of Disease project, AD is one of the 50 most prevalent diseases worldwide and has the second highest disability ranking of all nonmalignant skin diseases (Hay et al 2014).

The clinical pattern of AD varies with age and generally develops during the first 5 years of life in 90% of patients (but not in the first weeks of life, as seen in the autosomal dominant hyper-immunoglobulin E syndrome; Lyons et al 2015). Infants usually show acute erythematous and often exudative papules on the face or scalp, which are often intensely pruritic. The childhood phase (2 years of age to puberty) and adult phase of AD tend to have less acute or exudative lesions but instead typically present with more lichenified and localized lesions (flexural folds, the face and neck, the upper arms and back, and the dorsa of the hands, feet, fingers, and toes), which represent a more chronic stage of the condition (Akdis et al 2006). The unifying and cardinal feature of all presentations of AD is the pronounced and often unbearable itching.

In addition to the allergy-related sequelae of AD affecting the skin, recent reports have shown that children with AD, compared to those without AD, are at a higher risk of developing psychosocial comorbidities such as attention-deficit/hyperactivity disorder and depression (de la O-Escamilla and Sidbury 2020, Hong et al 2019, van der Schans et al 2017, Yaghmaie et al 2013). Sleep disturbance, both in pediatric patients and their parents/caregivers, is also common and can significantly impair quality of life (Chang and Chiang 2018, Ramirez et al 2019, Yang et al 2019).

Despite the availability of a number of treatment options, there is still a significant medical need for safe topical therapies that provide rapid and effective control of the signs and symptoms of AD and that are also both effective and safe, particularly in children. Moderate to potent topical corticosteroids and calcineurin inhibitors have well-known safety restrictions limiting their use to 4 and 8 weeks, respectively. In addition, a PDE4 inhibitor, 2% crisaborole (Eucrisa[®]) ointment, was recently approved in the United States for patients aged 3 months and older with mild to

moderate AD and has no such safety limitations but was shown to have modest efficacy ([Eucrisa 2020](#)).

For patients with more severe AD, the most recent addition to the systemic drug armamentarium is dupilumab ([Dupixent® 2020](#)). Dupilumab is a monoclonal humanized antibody against IL-4R α that blocks the action of IL-4 and IL-13 and was approved for adult patients with moderate to severe AD in 2017 and most recently in children aged 6 years and older in the United States ([Dupixent 2020](#)).

Studies with oral JAK inhibitors (tofacitinib and baricitinib) indicated that these drugs may be effective in the treatment of patients with AD ([Levy et al 2015](#), [Napolitano et al 2020](#)) and have triggered further interest in their use as topical agents for this skin condition. A clinical study with topical tofacitinib confirmed that JAK inhibitors can be effective in AD also when used topically ([Bissonnette et al 2016](#)). Consequently, efforts have been made to find new treatment possibilities that would more appropriately address the medical needs of patients with AD.

Janus kinases are intracellular signaling enzymes that act downstream of key proinflammatory cytokines known to promote the pathogenesis of AD. Ruxolitinib (INCB018424) is a potent and selective JAK1 and JAK2 inhibitor that is currently approved for use in tablet form for the treatment of patients with myelofibrosis and polycythemia vera in multiple countries and acute graft-versus-host disease in the United States. Recent studies suggest that JAK inhibition may have antipruritic effects by acting directly on sensory nerve fibers and may offer a novel therapeutic approach with dual anti-inflammatory and antipruritic properties.

Nonclinical pharmacology, PK/PD, and toxicology data for ruxolitinib cream from in vitro and in vivo model systems support the use of topically applied ruxolitinib cream for the treatment of patients with AD, psoriasis, vitiligo, and other inflammatory diseases of the skin. Refer to the [ruxolitinib cream IB](#) for a summary of findings from the nonclinical studies.

2.2. Pivotal Phase 3 Studies and Pilot Pediatric Study

2.2.1. INCB 18424-303 and INCB 18424-304: Phase 3 Adolescent/Adult Studies

The ruxolitinib cream Phase 3 studies (INCB 18424-303 and INCB 18424-304) confirmed that 1.5% ruxolitinib cream applied BID for 8 weeks is a highly effective treatment for participants with AD and is not associated with safety concerns. A lower strength of ruxolitinib cream (0.75% BID for 8 weeks) was also investigated in these trials. While its safety profile was not different from that of 1.5% cream, it was less efficacious than the higher strength.

